# Improving Blood Pressure Control in Diverse Populations by Measuring Accurately, Acting Rapidly, and Partnering with Patients: the BP MAP Study Protocol

## I. EXECUTIVE SUMMARY

BP-MAP is a cluster randomized controlled trial (RCT) designed to compare the effectiveness of BP lowering from a clinic-based quality improvement program with Full Support (dedicated practice facilitation) vs. a Self-Guided version of the program. The American Medical Association (AMA) developed the framework for the interventions. The trial will be conducted within the National Patient-Centered Clinical Research Network (PCORnet) that enables distributed querying of electronic health record data in a common data model. The primary outcome will be change in clinic-level blood pressure (BP) control at 6 months. Secondary outcomes will include other blood pressure (BP) control metrics, other time points (12 and 18 months), and process measures such as BP measurement accuracy, medication intensification, and average systolic blood pressure (SBP) reduction after a medication intensification, and repeat visit within 4 weeks after a visit with elevated BP. We will also conduct non-randomized comparisons of BP control in the Full Support and Self-Guided intervention arms to BP control in healthcare organizations in PCORnet not participating in an intervention arm (“Usual Care organizations”). To gain insight into sustainability of the program (self-guided and full-support), we will perform a limited program evaluation to examine stakeholder satisfaction and assess barriers and facilitators to implementation as well as their willingness to continue program-related activities beyond the study period. We have obtained a certification of exemption from IRB oversight given that both arms will implement accepted guideline-based minimal risk quality improvement interventions.

## II. BACKGROUND

Uncontrolled BP is the leading preventable cause of death in the US after smoking, causing nearly 400,000 deaths per year. While effective medications are available to control BP, multiple rounds of medication adjustment and intensification are typically required, and BP control is often not achieved.

The usual configuration of healthcare delivery – periodic and relatively infrequent office visits with a physician – is not ideal for achieving BP control quickly and efficiently. In-office measurement of BP is often performed using poor technique, while the patient is getting settled after arrival at the office. Due to these reasons and the “white coat effect”, it is often artificially elevated and may not be a reliable indicator of actual BP. Inaccurate BP measurement may result in missed opportunities for BP treatment intensification, which is common in the US, and a major cause of delay in attainment of BP control. Patients’ lack of adherence to BP medications is also a common cause of delay in control. While discontinuation of medications is sometimes due to medication side effects, it may also result from a lack of adequate time and attention paid to shared decision-making about the need for treatment intensification.

Some healthcare organizations have successfully reconfigured the way they deliver care for hypertension and manage their hypertensive patient population. Kaiser Permanente Northern California, for example, achieved BP control rates of 80% by using population management, frequent non-physician visits and evidence-based treatment protocols for optimal treatment intensification (). Other programs utilize pharmacists and nurses as case managers to provide medication management between visits. Reconfiguring services with additional staff dedicated to medication and disease management programs, however, may not be feasible or sustainable in all settings, particularly in

resource-poor settings such as safety net clinics. Deployment of sustainable programs may enhance clinic-based BP management.

The AMA developed a framework for clinic-based quality improvement that works within traditional office-based configuration of healthcare delivery (the “Measure Accurately, Act Rapidly, and Partner with Patients” (M.A.P.) Program, described below). The AMA is collaborating with AHA in the initiative, “Target:BP” to 1) recognize health care organizations achieving  $\geq 70\%$  BP control and 2) improve BP control by scaling the M.A.P. program to build a healthier nation. The initiative includes a set of tools, resources and detailed plans to support clinics interested in implementing the M.A.P framework as a structured intervention program.

Pilot implementation of this program led to dramatic improvements in BP control (from 63% to 90% in a single clinic and 64% to 74% in a group of 16 clinics). Although these results are promising, questions remain regarding how to optimize and efficiently scale the program in order to maximize sustained clinic-level involvement remain.

In this study, we will randomize 20-28 clinics to receive one of two types of support interventions: 1) a set of self-evaluation tools, improvement plans, and other resources that can be accessed by clinics and used independently (“Self-Guided”), and 2) a practice facilitation support program that helps clinics understand those tools/plans/resources and actually train people to implement the tools and plans (“Full Support”). We will then compare BP control between those arms, and against Usual Care control organizations. Additionally, we will perform a limited program evaluation to examine stakeholder satisfaction and assess barriers and facilitators to implementation as well as their willingness to continue program-related activities beyond the study period.

### III. METHODS

#### Aim

To compare effectiveness of the M.A.P. program with “Full Support” (dedicated practice facilitation) versus a “Self-Guided” version (online access to M.A.P. materials and orientation webinar only). A secondary aim is to compare these active interventions to usual care.

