#### Hypothesis

We hypothesize clinics randomized to the Full Support version will achieve a larger increase from baseline in the proportion of their hypertensive patients with controlled BP at 6 months as compared to clinics randomized to the Self-Guided version, and also as compared with usual care.

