### **Analysis Plan**

Overview: We will use an unadjusted difference-in-differences analytic approach to testing comparative effectiveness hypotheses, weighting for differences in cluster size. Despite expected between-clinic differences in baseline characteristics and BP control (especially in the non-randomized comparison with Usual Care control organizations), the difference-in-differences approach provides some protection against confounding because the outcome being compared is a within-clinic change score, as described below. We will first conduct 3 pairwise primary hypothesis tests (adjusting for multiple comparisons), as described below. We will then conduct a series of exploratory analyses of secondary outcomes, sensitivity analyses adjusting for baseline clinic-level characteristics, subgroup analyses to examine heterogeneity of effect, and exploratory mediation analyses to understand the mechanisms by which the full-support intervention might provide greater effectiveness.

Differences-in-differences analytic approach: We will calculate difference-in-differences through the following steps:

1. Use clinic-level metrics (e.g., % BP control) at baseline for each clinic before the intervention starts ( $t_0$ ) and then including the 6th full month of the intervention (" $t_6$ ", noting that the period will actually be 7 months offset for the Intervention Clinics and 6 months for the Usual Care Clinics; see Outcomes and Measurements, above)
2. Calculate the clinic-level pre-post difference in the metric ( $t_6 - t_0$ )
3. Calculate the mean pre-post difference in each treatment group, the between-group difference of differences, both with 95% confidence intervals, and compare the 20-28 pre-post differences by arm using weighted linear regression; observations will be weighted by the inverse of the site-specific variances of the change scores, which will be approximated using the site-specific sample size and level of the time-specific metrics, and the average correlation of the pre- and post-metrics across clinics. Weights will be normalized to sum to the total number of clinics in the Arm 1 vs. Arm 2 comparisons (and to the number of included clinics plus the number of participating PCORnet datamarts for the comparisons of each Arm with Usual Care).

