### Primary hypothesis tests, with adjustment for multiple comparisons

Our primary hypothesis tests will be 3 pairwise comparisons:

- Test 1: Arm 1 vs Arm 2
- Test 2: Arm 1 vs. Usual Care
- Test 3: Arm 2 vs. Usual Care

In order to maintain an overall type 1 error rate of 5%, we will set our critical p-value threshold for Test 1 at  $p=0.04$ , and then at  $p=0.005$  for Test 2 and Test 3 since they will benefit from the very large sample size expected in the Usual Care groups. No other adjustments for multiple comparisons are planned for secondary outcomes or other exploratory analyses described below.

**Descriptive analyses comparing clinic-level baseline characteristics:** *Descriptive statistics* will be used to compare clinic-level characteristics between the two intervention arms at baseline. We will include descriptions of clinic-level patient population characteristics (age groups, gender, race/ethnicity, type of insurance, mean number of current antihypertensive medication classes prescribed, and prevalence of comorbid conditions such as diabetes, chronic kidney disease, or heart failure), workforce composition (i.e. proportion of nurse practitioners, physician assistants, physicians, and physician specialty - internal vs family medicine), clinic size and staffing level (total number of patients, nurses, and medical assistants), level of access (availability of same-day appointments, mean time to third next available appointment), and possibly other characteristics depending on availability.

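### Usual Care comparisons are a secondary aim in the Aim but two of three primary tests in the analysis plan, and no rule says which test decides the primary conclusion

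*Combined protocol and SAP*

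**What the plan says.** All references are to the combined protocol and SAP.

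- **Aim.** The main aim is Full Support versus Self-Guided. Usual care follows: "A secondary aim is to compare these active interventions to usual care".
- **Executive Summary.** After the primary and secondary outcomes, it adds: "We will also conduct non-randomized comparisons of BP control in the Full Support and Self-Guided intervention arms", set against organisations outside both arms.
- **Hypothesis.** Full Support is expected to give the larger increase in control at 6 months "as compared to clinics randomized to the Self-Guided version, and also as compared with usual care". The two comparisons are not ranked, and Self-Guided versus usual care is not mentioned.
- **Analysis Plan, overview.** "We will first conduct 3 pairwise primary hypothesis tests (adjusting for multiple comparisons), as described below". It also expects baseline differences between clinics, "especially in the non-randomized comparison with Usual Care control organizations", and claims only partial protection from the difference-in-differences approach.
- **Primary hypothesis tests.** "Our primary hypothesis tests will be 3 pairwise comparisons": Test 1 is Arm 1 versus Arm 2, and the others are "Test 2: Arm 1 vs. Usual Care" and "Test 3: Arm 2 vs. Usual Care". Thresholds are 0.04 for Test 1 and 0.005 each for Tests 2 and 3, to hold overall type 1 error at 5%.
- **Sample size and power.** With 10 clinics per arm and an SD of change of 4.4 points, power for Full Support versus Self-Guided is given as 83% for a 6-point difference and 92% for 7 points. Neither alpha nor sidedness is given.

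**The concern.** The same comparisons cannot be both a secondary aim and primary tests, and no other section settles which they are. The label matters for two reasons.

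First, Tests 2 and 3 have their own alpha and do not wait on Test 1. As written, a significant comparison with Usual Care has primary status whatever the randomised comparison shows. These comparisons are open to biases that alpha control does not address:

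- Active clinics come from two networks chosen to focus on safety-net care. Usual Care comes from other networks (Study Population and Setting).
- The Usual Care units are datamarts, not clinics (Usual Care Clinics; Analysis Plan, step 3).
- Baseline and follow-up measurement periods are 6 months apart for Usual Care and 7 months apart for the intervention clinics (Outcomes and measurements).

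Second, keeping Tests 2 and 3 in the primary family takes 0.01 of alpha from the only randomised comparison, which answers the main aim.

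**Working it through.** **1. Status of the Usual Care comparisons, section by section**

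| Section | Status |
|---|---|
| Executive Summary | additional, non-randomised |
| Aim | secondary |
| Hypothesis; Study design | mentioned, not ranked |
| Outcomes and measurements | primary outcome defined for Usual Care sites too |
| Analysis Plan overview; Primary hypothesis tests | primary, with allocated alpha |

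No section gives a testing order or a decision rule across the three tests.

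**2. The alpha split**

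0.04 + 0.005 + 0.005 = 0.05. The Bonferroni bound therefore holds whatever the correlation between tests, and the plan's 5% is reproduced. Simulation under the global null with shared arms gave about 0.045 to 0.046 (SD 4.4 in every group; 20 or 50 datamarts assumed, as the number is not stated).

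**3. Power of Test 1**

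Inputs from Sample size and power: n = 10 per arm, SD = 4.4, difference d = 6 or 7. Assumption: two-sided test, unweighted.

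- Standard error = 4.4 × √(2/10) = 1.968.
- Noncentrality = d / 1.968, which is 3.049 for 6 points and 3.557 for 7 points.
- t-test power ≈ P(T > t_crit), with T noncentral t on 18 df. t_crit is 2.101 at 0.05 and 2.214 at 0.04.
- Normal approximation ≈ Φ(noncentrality − z_crit). z_crit is 1.960 at 0.05 and 2.054 at 0.04.

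| Method and alpha | 6 points | 7 points |
|---|---|---|
| Stated in the plan | 83% | 92% |
| t-test, 0.05 | 82.2% | 92.0% |
| t-test, 0.04 | 79.2% | 90.1% |
| Normal approximation, 0.05 | 86.2% | 94.5% |
| Normal approximation, 0.04 | 84.0% | 93.4% |

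The t-test at 0.05 is the closest match, but the normal approximation at 0.04 is within 2 points of both stated figures. The alpha behind them cannot be recovered with certainty.

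**4. Cost of 0.04 instead of 0.05 (t-test)**

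- 10 per arm: 82.2 − 79.2 = 3.0 points of power at a 6-point difference, and 92.0 − 90.1 = 1.9 at 7 points.
- 14 per arm, the upper end allowed under Randomization: 93.5 − 92.0 = 1.5 points at a 6-point difference.
- Difference detectable with 80% power at 10 per arm: 5.83 points at 0.05 and 6.06 at 0.04.

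**5. Illustration of what alpha control does not cover**

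Assumptions, none from the plan except the SD and the 10 clinics per arm: no intervention effect, SD 4.4 in every group, unweighted t-tests, 20 or 50 datamarts, and a secular drift that differs between active clinics and Usual Care.

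| Differential drift | Test 2 or 3 significant, 20 datamarts | 50 datamarts |
|---|---|---|
| 0 points | at most 1% (0.005 + 0.005) | at most 1% |
| 2 points | 7.9% | 11.5% |
| 3 points | 21% | 31% |

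Test 1 stays at about 4% throughout. The size of any real drift is unknown, so the table shows sensitivity and does not predict a rate.

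**The case against.** The strongest reply is that the Aim sentence is the outlier. The Hypothesis puts Full Support versus usual care beside the randomised comparison, Study design names usual care as a comparator, Outcomes and measurements applies the primary outcome to Usual Care sites, and the analysis plan allocates alpha in advance. On that reading the Aim is the text to correct. This stands as far as it goes: either direction resolves the contradiction, but one must be chosen.

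The plan also ranks the tests in practice. Test 1 holds 0.04 of the 0.05, and only Test 1 has power figures for the main effect. That shows intent, but it is not a decision rule.

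A reader might infer that a significant Test 2 or 3 would by itself make the trial positive. The documents do not say so: no such success rule is written, each test answers its own question, and the non-randomised status is disclosed. What they leave open is whether it could be read that way.

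A reader might also infer that the power calculation ignored the alpha split. The figures do not establish that, since a normal approximation at 0.04 also comes close and the plan says simulations confirmed its results.

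The absence of a hypothesis for Self-Guided versus usual care is minor. The Aim covers both active interventions, and a two-sided test needs no directional hypothesis.

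The power cost is small. At 11 per arm the t-test at 0.04 gives 83.5% and 93.0%, already above the stated figures.

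**Conclusion.** The contradiction between the Aim and the analysis plan is real, and no other section resolves it. As written, two non-randomised comparisons have primary status independent of the randomised Test 1, with no statement of which test carries the primary conclusion. It is not a type 1 error problem: the split holds 5%.

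The measurable cost to Test 1 is about 3 points of power at a 6-point difference and 2 at 7 points with 10 clinics per arm, and about 1.5 at 6 points with 14. This assumes a two-sided, unweighted t-test with SD 4.4. The larger issue is interpretive, because the primary label would rest on comparisons for which the plan itself expects confounding. The point should be settled in the text before arms are compared. It does not undermine the randomised comparison.

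**What to change.** Reconcile the Aim, the Hypothesis, the Analysis Plan overview and the primary hypothesis tests section, in one of two ways.

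1. **Follow the stated Aim.** Name Test 1 as the sole primary test at two-sided 0.05. List Tests 2 and 3 as secondary, non-randomised comparisons reported with confidence intervals.
2. **Keep three primary tests.** Amend the Aim to say so. State that conclusions about level of support rest on Test 1, and that a significant Test 2 or 3 alone is non-randomised evidence and does not make the trial positive.

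In either case, give the alpha, sidedness and method behind the power figures, and restate them at the Test 1 threshold actually used. If 0.04 is kept with 10 clinics per arm, the t-test figures are about 79% and 90%.

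The cost is wording only, with no change to data collection. The downside is that Usual Care results lose the primary label under option 1, or carry a caveat on it under option 2.

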#### Hypothesis

We hypothesize clinics randomized to the Full Support version will achieve a larger increase from baseline in the proportion of their hypertensive patients with controlled BP at 6 months as compared to clinics randomized to the Self-Guided version, and also as compared with usual care.

#### Study design

This is a pragmatic, cluster-randomized, comparative effectiveness trial designed to compare the effectiveness of the M.A.P. program with Full Support versus a Self-Guided version of the program, and versus usual care.

#### Study Population and Setting

We will recruit Active Clinics from REACHNet and ADVANCE, two of the 10 Clinical Data Research Networks (CDRNs) that comprise PCORnet. We chose these two CDRNs to focus clinic recruitment in safety net clinics and to boost numbers of underserved populations and enhance power to detect heterogeneity of treatment effects. We are targeting clinics that have varied racial/ethnic composition with substantial proportions of Hispanic and Black patients, and patients with lower socioeconomic status. Usual Care Clinics will come from other CDRNs within PCORnet.

### Active Clinics

For inclusion as an Active Clinic in this study, clinics may participate must be able to identify:

- A Site Champion who works at the clinic and who is willing to take primary responsibility for implementing the M.A.P. intervention
- A Physician Champion who works at the clinic and who is willing to advocate actively for the M.A.P. intervention
- A Practice Change Facilitator willing to attend a 1-day training and help guide implementation of the M.A.P intervention for Full Support sites, with the support of AMA staff (may be the Site Champion or Physician Champion, or a person with regional responsibilities who can support multiple sites)

Sites will be excluded if they:

- Have implemented any high blood pressure quality improvement component from the M.A.P. BP improvement program as part of Target: BP or from the AMA or Target: BP websites
- Are currently involved in an ongoing clinical trial or grant funded project related to high blood pressure or hypertension

### Usual Care Clinics

We will include PCORnet Datamarts participating in BP TRACK, a concurrently-running BP Control Registry within PCORnet that will provide quarterly datamart-level estimates of BP control and other aggregate metrics relevant to BP control. All participating datamarts will be included, with the following exceptions:

- We will exclude datamarts with any Active Clinics participating in BP MAP
- We will exclude datamarts that obscure dates via date-shifting, as this will not allow for control of concurrent secular trends

### Patients

Within clinics (Active or Usual Care), patients will be eligible (and identified from the electronic health record) if they meet National Quality Forum BP Control Metric (NQF 0018) criteria:

- Age 18-85 on the date of analysis
- At least one outpatient encounter with a diagnosis of hypertension during the first six months of the measurement year (ending on the date of analysis)
- No diagnosis or evidence of end-stage renal disease on or prior to the end of the measurement year
- No pregnancy during the measurement year
- No admission to an inpatient setting during the measurement year

### **Interventions**

This trial will compare two strategies for improving BP control at the clinic level and compare these two strategies to a group of non-randomized usual-care clinics. Both strategies rely on an extensive set of materials developed by the AMA to support clinic implementation of the M.A.P. Program. These materials have been tested, validated and include clinician and patient targeted resources. We will compare two different ways of helping clinics use these materials to implement the M.A.P. Program:

**Arm 1: Self-Guided:** Active Clinics randomized to the Self-Guided Arm will receive access to an AHA/AMA web platform that includes the posted M.A.P. materials as described in the appendix and limited access to AMA Staff who are available to answer questions. We will facilitate access

to staff by hosting a kick-off webinar for program participants that will include an orientation to the materials on the website, general advice and practical tips about what works for implementation, and time for answering questions and discussion with the group.

**Arm 2: Full Support:** Active Clinics randomized to the Full Support Arm will receive online access to M.A.P. materials and orientation webinar, as described above, but also a Practice Facilitator (personnel trained to implement the M.A.P. BP Improvement Program) who will be supported by AMA staff, and will lead the health center clinical staff, site champions and physician leads at each clinic over the course of 6 months to support the implementation of the MAP Program. With support from an AMA “Improvement Advisor”, the Practice Change Facilitators will perform a baseline assessment of current workflows and assess each domain of M.A.P. They will 1) identify gaps and plan for specific incremental modifications tailored to address specific clinic needs; 2) perform periodic evaluations with the AMA Improvement Advisor to monitor use of M.A.P assessment tools and checklists; and 3) support use of EHR-based reporting that displays clinic-level BP control and secondary outcome measures. The goal of the Full Support program is to help care teams develop skills and sustainable workflows that are effective at attaining and maintaining high levels of BP control.

**Usual Care:** Usual Care Clinics will receive no intervention.

